7.8.4 Reporting of unanticipated adverse device effects

The Investigator shall submit to the Sponsor and to the reviewing IRB, a report of any unanticipated adverse device effect occurring during the study as soon as possible, but no later than 10 working days after the Investigator first learns of the effect (see US requirement 21 CFR 812:150 (a.)).

7.8.5 Pregnancy Reporting

A pregnancy confirmed during the study period must be reported by the Investigator on a pregnancy report form immediately upon knowledge of the pregnancy and the form must be submitted to the CRO according to contact details specified in Section 7.8.2. The report can be prospective or retrospective. Follow-up shall be conducted to obtain outcome information on all prospective reports.

Cases that led to fetal distress, fetal death or a congenital abnormality or birth defect, are to be regarded as SAEs and shall be reported on the exposure *in utero* report form to the Sponsor immediately but no later than 24 hours after the Investigator's awareness. These events shall be handled as SAEs during data processing. Other complications during the pregnancy that are related

Print date:

2022-06-13 07:02

to the pregnant woman which fulfil any serious criteria, such as pre-eclampsia requiring hospitalization, shall be reported and handled as SAEs. Elective abortions without complications shall not be reported as AEs.

7.8.6 Follow-up of unresolved events ongoing at termination of the study

All serious as well as non-serious AEs with a causal relationship to the study device or treatment procedure and ongoing at study end, shall be followed up after the subject's participation in the study is over. Such events shall be followed-up after the last study visit until resolved, assessed as chronic or stable, or the subject is lost to follow-up. Follow-up information shall be reported on the AE follow-up form.

7.8.7 Reporting and follow-up of events occurring after subject termination of the study

All AEs with a causal relationship to the study device or treatment procedure that the Investigator becomes aware of, serious as well as non-serious, with onset after the study termination (subject's last study visit) shall be reported to the Sponsor. The report should as a minimum include the information described in Section 7.7. The report can be sent via e-mail according to contact details specified in Section 7.8.2. The events shall thereafter be followed-up until resolved, considered chronic or stable, or the subject is lost to follow-up.

Device deficiencies 7.9

7.9.1 **Definition of a device deficiency**

A device deficiency is defined as an inadequacy of a medical device with respect to its identity, quality, durability, reliability, safety^d, or performance.

Note: Device deficiencies include malfunctions, use errors, and inadequate labelling.

Recording instructions 7.9.2

When a device deficiency is discovered, Part A of the clinical study complaint form must be completed by the Investigator and the source data recorded in the eCRF. The type of complaint must be described and injury to the subject or user, or unintended exposure to study device, must be reported as applicable. If an injury has occurred, an AE or an SAE form must be completed as applicable (refer to Section 7.8). If no SAE was experienced as a result of the device deficiency, the Investigator must assess whether or not the device deficiency could have led to an SAE if:

- Suitable action had not been taken,
- Intervention had not been made or,
- Circumstances had been less fortunate

In Part B of the clinical study complaint form, the Sponsor will make the same assessment.

7.9.3 Reporting of device deficiencies

The Investigator must send the completed clinical study complaint form to the CRO.

A device deficiency that led to a SAE and any device deficiency that could have led to a SAE must be reported to the CRO within 24 hours after the Investigator's awareness (for contact information, see Section 7.8.2). If the form is completed within the eCRF system, refer to the eCRF completion guidelines.

d Inadequacy of device safety refers to properties of the device which could have or have led to an AE.

If the Investigator or the Sponsor assesses that the device deficiency could have led to a SAE, the Sponsor is responsible for reporting the device deficiency to RA and the Investigator is responsible for reporting it to the IRB.

The deficient study device shall be retained by the study site until the Sponsor has confirmed whether the device shall be returned to the Sponsor for further evaluation, or if it can be destroyed at the study site.

7.10 Independent data monitoring committee

Not applicable to this study.

DESCRIPTION OF STUDY VISITS

A description of the study visits is provided in the

A written signed informed consent (including Health Insurance Portability and Accountability Act of 1996 (HIPAA)) must be obtained prior to performing any study-related evaluations and/or procedures. The subject must be provided with a fully completed dated and signed copy.

Visit 1 - Screening (Day -30 to Day 1) – all subjects

The following activities and screening assessments will be performed within 30 days prior to baseline.

Note: The screening visit and baseline visit (Day 1) may be performed on the same day.

- Obtain Informed Consent prior to conducting any study specific procedure.
- Assess eligibility: Review inclusion/exclusion criteria.
- Perform Urine Pregnancy test for all females of childbearing potential. Test result must be negative for the subject to be eligible for the study.
- Obtain demographic and baseline data: date of birth, height, weight, cup size, ethnicity, race and Fitzpatrick Skin Type (FST).

- o FST is a skin classification system that categorizes different skin colors, and their reactions to ultraviolet (UV) light.(21) For determination of the FST, see Table 4.
- o Height and cup-size may be self-reported, weight must be measured at the clinic.
- Record the subject's medical history (including any prior dermatological procedures or breast procedures (e.g. augmentation, implants, breast reduction surgery)).
- Record the subject's prior and concomitant therapies.
- CCI
- GDS assessment Treating Investigator.
- Schedule the baseline treatment visit (Day 1) if performed on a different day than screening.

8.2 Visit 2a, Baseline and First Treatment (Day 1) - all subjects

The screening visit and baseline visit (Day 1) may be performed on the same day. *If the screening visit and baseline visit are performed on the same day assessments will not be duplicated.*

Assessments prior to treatment:

- Re-confirm eligibility criteria
- Obtain weight measured at clinic.
- Review for changes in concomitant therapies.
- Perform Urine Pregnancy test for all females of childbearing potential (prior to treatment). Test result must be negative for the subject to be eligible for treatment.
- Record the subject's medical history
- Randomize the subject.

Obtain Photography

•	CCI	
		ı

• GDS assessment – Treating Investigator

Once the subject is deemed eligible for treatment by the Treating Investigator, the following procedures should be completed:

- Sculptra administration
- Evaluate the subject for post-treatment AEs Treating Investigator.
- Evaluate for device deficiencies.
- Dispense diary and instruct subject on daily diary completion. Remind subject to bring the diary to the next on-site visit.

	Title 43USSA2112 CIP Sculptra Decolletage	Doc id
GALDERMA	43055A2112 CIT Sculptra Deconetage	MA-50966

8.2 Visit 3a, Treatment 2/Follow-up (1 month [+ 2 weeks] after Treatment 1) - all subjects

Assessments prior to treatment:

- Re-confirm eligibility criteria.
- Review for changes in concomitant therapies.
- Perform Urine Pregnancy test for all females of childbearing potential (prior to treatment, if applicable). Test result must be negative for the subject to be eligible for treatment.
- Obtain Photography.
- AE assessment.
- Collect subject diary from treatment 1.
- GAIS assessment Treating Investigator and Subject.
- GDS assessment Treating Investigator.
- Schedule the next on-site visit (1 month [+ 2 weeks] after Treatment 2). Treatment and assessments post-treatment, for subjects who receive a second treatment:
- Sculptra administration (optional).
- Evaluate the subject for post-treatment AEs Treating Investigator.
- Evaluate for device deficiencies.
- Dispense diary and instruct subject on daily diary completion. Remind subject to bring the diary to the next on-site visit. (If applicable, if a second treatment is administered.)

[figure not shown]

2022-06-13 07:02

Print date:

Effective date: 2022-05-31 12:16

	Title	Doc id
	43USSA2112 CIP Sculptra Decolletage	200.00
GALDERMA	•	
EST, 1981		MA-50966

Visit 4a, Treatment 3/Follow-up (1 month [+ 2 weeks] after Treatment 2) - all subjects

Assessments prior to treatment:

- Re-confirm eligibility criteria.
- Review for changes in concomitant therapies.
- Perform Urine Pregnancy test for all females of childbearing potential (prior to treatment, if applicable). Test result must be negative for the subject to be eligible for treatment.
- Obtain Photography.
- AE assessment.
- Collect subject diary from treatment 2 (if applicable, if a second treatment was administered).
- GAIS assessment Treating Investigator and Subject.
- GDS assessment Treating Investigator.
- Schedule the next on-site visit (1 month [+ 2 weeks] after Treatment 3). Treatment and assessments post-treatment, for subjects who receive a third treatment:
- Sculptra administration (optional).
- Evaluate the subject for post-treatment AEs Treating Investigator.
- Evaluate for device deficiencies.
- Dispense diary and instruct subject on daily diary completion. Remind subject to bring the diary to the next on-site visit. (If applicable, if a third treatment is administered.)

GALDERMA

Title
43USSA2112 CIP Sculptra Decolletage

MA-50966

8.8 Visit 5a, Treatment 4/Follow-up (1 month [+ 2 weeks] after Treatment 3) – all subjects

Assessments prior to treatment:

- Re-confirm eligibility criteria.
- · Review for changes in concomitant therapies.
- Perform Urine Pregnancy test for all females of childbearing potential (prior to treatment, if applicable). Test result must be negative for the subject to be eligible for treatment.
- Obtain Photography.
- CCI
- AE assessment.
- Collect subject diary from treatment 3 (if applicable, if a third treatment was administered).
- GAIS assessment Treating Investigator and Subject.
- GDS assessment Treating Investigator.

CCI

• Schedule the next on-site visit at Month 6 (+2 weeks) after Baseline.

Treatment and assessments post-treatment, for subjects who receive a fourth treatment:

- Sculptra administration.
- Evaluate the subject for post-treatment AEs Treating Investigator.
- · CCI

Doc id 43USSA2112 CIP Sculptra Decolletage GALDERMA **MA-50966**

- Evaluate for device deficiencies.
- Dispense diary and instruct subject on daily diary completion. Remind subject to bring the diary to the next on-site visit. (If applicable, if a fourth treatment is administered.)

8.11 Visit 6, Safety follow-up (1 month [+ 2 weeks] after Treatment 4) – for subjects that received treatment at Visit 5a.

- Review for changes in concomitant therapies.
- AE assessment.
- Collect and review subject diary.

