3.5 Randomization

Before starting the study, a randomization list will be prepared under the supervision of a designated statistician from the Sponsor. Approximately 30 adult female subjects will be randomized 1:1 to receive either *Sculptra* reconstituted with 8 mL SWFI with the addition of 1 mL 2% lidocaine HCl or *Sculptra* reconstituted with 17 mL SWFI with the addition of 1 mL 2% lidocaine HCl. Subjects will be stratified by GDS severity score and study center. Randomization numbers will be allocated in ascending sequential order to each subject.

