3.6.1 Emergency unblinding

Not applicable as the treating Investigator is not blinded to treatment.

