### 1.3 Effectiveness Assessments

For all assessments, baseline will be defined as the observation that is closest to but prior to study treatment on Day 1. Change from baseline will be calculated as the value at a given time point minus the baseline value.

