#### 1.3.1 Galderma Décolletage Scale (GDS)

The GDS is a 5-point validated scale used to assess lines and wrinkles. The scale assessment will be performed live by the Treatment Investigator at all visits.

CCI

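### When screening and treatment fall on separate days, the visible text lets the primary endpoint's baseline GDS be graded after randomisation by an investigator who knows the arm

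*Protocol*

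**What the plan says.** Screening and baseline may be on the same day or on different days. Protocol 8.1 (Visit 1) includes a GDS by the Treating Investigator and ends with the instruction "Schedule the baseline treatment visit (Day 1) if performed on a different day than screening".

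Protocol 8.2, Visit 2a, has a block of assessments to be done before treatment. Within it, "Randomize the subject" comes first, then photography and a redacted item, then "GDS assessment – Treating Investigator". For same-day visits the section adds: "If the screening visit and baseline visit are performed on the same day assessments will not be duplicated".

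On allocation, Protocol 3.5 states: "Subjects will be stratified by GDS severity score and study center". On blinding, Protocol 3.6.1 states: "Not applicable as the treating Investigator is not blinded to treatment".

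In the SAP, section 1.3.1 has the GDS "performed live by the Treatment Investigator at all visits", and section 1.3 states that "baseline will be defined as the observation that is closest to but prior to study treatment on Day 1". SAP 1.3.2 has the GAIS rated against a photograph from the baseline visit, taken before the first treatment.

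**The concern.** A responder is a subject who improves by at least one grade from baseline, so the baseline grade counts as much as the Month 9 grade. If the Treating Investigator grades on Day 1 already knowing which reconstitution volume the subject will receive, that knowledge can influence the grade. For example, a subject who is truly grade 2 but is recorded as 3 becomes a responder without changing. A subject who is truly grade 3 but is recorded as 2 stops being a responder after a true one-grade improvement.

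If such errors differ by arm, they distort the responder rate of each arm and the between-arm difference that Protocol 9.4 plans to present with a 95% confidence interval. Comparing the two groups is a secondary effectiveness objective in the protocol's section on objectives, and Protocol 1.2 says the data will support a pivotal study. The baseline photographs are exposed in the same way, although a photograph leaves less room for judgement than a grade.

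**Working it through.** The plan gives no figure on this point to reproduce. The check is a reading of the sequence, followed by an illustration of scale.

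**Sequence, separate-day visits**

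1. A GDS is recorded at screening (Protocol 8.1) and another on Day 1 (Protocol 8.2, Visit 2a; SAP 1.3.1 agrees).
2. The Day 1 score is the one closest to treatment, so under SAP 1.3 it is the analysis baseline. The screening score is not.
3. The visible condition on the Day 1 score is that it precedes treatment. Nothing visible requires it to precede randomisation, and the list places it afterwards.
4. Stratification by GDS severity needs some score before allocation. The screening score can meet that need, so stratification does not force the Day 1 score to come first. No visible text says which score sets the stratum.
5. The grader is unblinded (Protocol 3.6.1). The documents do not say at what moment the grader learns the arm.

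**Sequence, same-day visits**

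There is one GDS, it is not repeated, and it must exist before stratified randomisation. The baseline grade of these subjects is not affected.

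**Scale**

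Inputs: about 30 subjects randomised 1:1 (Protocol 3.5), taken as 15 per arm with no losses; Clopper-Pearson 95% intervals per group (SAP 2.4.3). The responder counts below are assumptions, because the documents give no expected rate.

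One reclassified subject: 1/15 = 6.7 points in that arm. For example, 9/15 = 60.0% becomes 10/15 = 66.7%.

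| Responders | Rate | 95% interval | Half-width (points) |
|---|---|---|---|
| 8/15 | 53.3% | 26.6 to 78.7 | 26.1 |
| 9/15 | 60.0% | 32.3 to 83.7 | 25.7 |
| 10/15 | 66.7% | 38.4 to 88.2 | 24.9 |
| 12/15 | 80.0% | 51.9 to 95.7 | 21.9 |

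One subject relative to the per-arm half-width: 6.67/26.1 = 0.26 and 6.67/21.9 = 0.30.

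Between-arm difference: Wald half-width = 1.96 × √(2p(1 − p)/15), with the same true rate p in both arms.

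- p = 0.5: 35.8 points; 6.67/35.8 = 0.19
- p = 0.6: 35.1 points; 6.67/35.1 = 0.19
- p = 0.7: 32.8 points; 6.67/32.8 = 0.20

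These figures give the weight of one subject, not an expected bias. An expected shift would need the share of separate-day visits, the misgrading rate by arm and the mix of grades 2 and 3. The documents state none of these.

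**The case against.** The strongest reply is that the order of bullets is not evidence of the order of events. These lists are not chronological elsewhere: Visit 1 puts the eligibility review near the top and the GDS near the end, although eligibility depends on the GDS. Visit 2a re-confirms eligibility as its first item, and a site could well grade the subject then. The body of Protocol 6.2, the Schedule of Assessments and an item in Visit 2a are not visible, and a timing rule may sit in any of them. All of this stands. It limits the point to what the visible text allows.

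A second reply is that every subject receives Sculptra and the investigator knows this from the start, so a general wish to show improvement can raise baseline grades before allocation as easily as after it. That also stands. Reordering removes only misgrading that depends on the arm. The documents show no motive for favouring one arm on effectiveness; Protocol 1.1 frames the larger volume mainly as a question of tolerability.

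A third reply is that the same unblinded investigator rates Month 9, which is the larger bias. That is true, and this change does not touch it. It does not excuse the baseline part, which can be avoided without any added procedure.

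A reader might infer that the eligibility rule and SAP Table 3 catch every baseline error except a swap between grades 2 and 3. They do not: both test the recorded grade, so a subject truly outside grades 2 and 3 but recorded within them passes.

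**Conclusion.** The point holds as a permitted sequence: on separate-day visits the visible text allows the primary baseline, and the GAIS comparator photograph, to be obtained after allocation by an assessor who is not blinded. It merits consideration as an inexpensive improvement in a descriptive pilot whose sample size has no statistical calculation behind it.

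The scale rests on the assumption of 15 per arm. A single reclassified subject is visible in an arm's rate but remains well inside the width of every planned interval.

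Two stronger readings are not supported. A reader might infer that the plan instructs sites to grade after randomisation; it only fails, in the visible text, to rule this out. A reader might also infer that the overall responder rate is biased. That would require arm-specific errors that do not cancel across arms, and nothing in the documents establishes this.

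**What to change.** For subjects not yet randomised, list the Day 1 GDS and the baseline photographs before the randomisation step in Protocol 8.2, Visit 2a. Leave the SAP 1.3 baseline definition and the existing source of the stratum unchanged, so that the definition and the stratification stay the same throughout the trial.

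Add to the SAP one sensitivity analysis of the Month 9 GDS responder rate by arm, with the screening GDS as baseline for separate-day subjects. Accompany it with a count by arm of subjects whose screening and Day 1 grades differ.

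If enrolment is complete, only the sensitivity analysis applies. That is possible: the SAP took effect on 2023-03-06, about nine months after Protocol v2.0 of 31 May 2022, against a planned 3 months of enrolment. The actual start of enrolment is not stated.

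The cost is a small protocol amendment, with the review that Protocol 10.4.3 requires, and one extra table. No visit or assessment is added. The screening GDS may be up to 30 days old and, as an entry-qualifying score, may itself be graded toward eligibility, so it should serve for sensitivity only.

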8.12 Visit 7, Follow-up (month 6 [+ 2weeks] after baseline) - all subjects

- Obtain weight measured at clinic.
- Review the subject's concomitant therapies.
- Obtain Photographs.
- Assess for AEs- Treating Investigator

Doc id 43USSA2112 CIP Sculptra Decolletage GALDERMA MA-50966

- GAIS assessment Treating Investigator and Subject.
- GDS assessment Treating Investigator.

8.13 Visit 8/Final visit/Early termination, (month 9 [±2 weeks] after baseline) - all subjects

- Obtain weight measured at clinic.
- Review the subject's concomitant therapies.
- Obtain Photographs.
- Assess for AEs- Treating Investigator

- GAIS assessment Treating Investigator and Subject.
- GDS assessment Treating Investigator.

8.14 Unscheduled Visits

- Unscheduled visits can be performed if necessary (for example in case of an AE requiring specific treatment).
- Unscheduled visits related to the study should be documented and all AEs must be captured.

STATISTICAL DESIGN AND ANALYSIS

9.1 General

A comprehensive Statistical Analysis Plan (SAP) with a detailed description of all statistical analyses will be developed.

All study data will be listed in subject data listings.

	Title 43USSA2112 CIP Sculptra Decolletage	Doc id
GALDERMA EST. 1981	•	MA-50966

All statistical analyses, including summary tables and data listings, will be performed using SAS. Confidence intervals will be two-sided and constructed at a confidence level of 95%.

All endpoints will be summarized descriptively. Continuous endpoints will be summarized using mean, median, standard deviation (SD), minimum and maximum values, for the observed value as well as the change from baseline. Categorical endpoints will be presented in frequency tables with number and percentage of observations for each level.

9.2 **Analysis populations**

The following populations will be defined:

•	Safety	Includes	all	subjects	who	were	treated	with	Sculptra.
	•	Subjects	are a	analyzed l	based	on the	as treate	ed prir	nciple (i.e.
		according	g to	the treatm	ent ac	tually	received	d).	

Intention-to-treat (ITT) Includes all subjects who were randomized based on the as randomized principle (i.e. according to the treatment they were randomized to).

Includes all subjects in the ITT who complete the visit 9 Per protocol (PP) months after baseline without any deviations considered to have substantial impact on the primary effectiveness outcome.

The ITT is the primary population for all effectiveness analyses. The primary effectiveness analysis will be repeated using the PP analysis set if there is at least a 10% difference in the number of subjects between the PP and ITT sets. Safety analysis is performed based on the safety population set. The disposition of subjects will be presented in tables and/or figures as appropriate.

9.3 Demographics, baseline assessments, and subject characteristics

Demographic endpoints, baseline assessments, and subject characteristics will be presented by treatment group, based on the ITT analysis set using descriptive statistics, as appropriate.

9.4 Effectiveness analysis

Continuous endpoints will be summarized using descriptive statistics, e.g. mean, median, SD, minimum and maximum values. Categorical endpoints will be presented in frequency tables with number and percentage of observations for each level.

Responder rate regarding GAIS and GDS will be presented together with a 95% confidence interval (based on the binomial distribution). The difference in responder rate regarding GAIS and GDS will be calculated between the two groups presented together with a 95% confidence interval.

No adjustment to the level of significance will be performed; p-values obtained for any endpoint other than the primary will only be provided for ease of interpretation of the results.

